3.0 Specimen Collection and Banking

Blood and saliva samples will be collected from participants in this study for the purpose of examining cortisol and endogenous oxytocin. Saliva will not be collected from participants with a BMI of ≥ 39 or from participants with an appointment start time later than 10:00am. Blood will be drawn by MUSC Research Nexus nursing staff, processed, and stored at the MUSC Research Nexus until ready for assay. Saliva will be collected by trained research staff only and transported to the MUSC Research Nexus for processing, storage, and assay. Only approved study staff will have access to data associated with specimens.

Note that saliva and/or blood samples may not be collected if the study team determines a contraindication exists that might affect study results (including recent consumption of caffeine or food, medications that affect oxytocin (e.g., androdgeli, levothyroxine, etc.) or other factors).

12.0 Data Management and Statistical Analysis Plan

Descriptive statistics will be used to characterize participants at each time point. Because the units of randomizations are dyads (i.e., couples), all analyses will account for potential within-dyad correlation (e.g., intraclass correlation [ICC]). Generalized linear mixed models (GLMMs) with random couple effects will be used to assess group differences in baseline characteristics. These can be operationalized using SAS Proc Mixed and Proc GLIMMIX. Should any variables

exhibit significant departures from normality, variable transformations (e.g., logarithmic) or non-parametric approaches will be used, as appropriate. GLMMs are ideal for handling analyses involving correlated measures¹⁰⁸, and they will allow us to estimate both the between- and within-couple variation. GLMMs are also useful for modeling longitudinal (repeated) outcomes on individual subjects, and the models can be adapted with appropriate link functions for continuous, binary, and count outcomes. GLMMs will be constructed for analyses involving group (or subgroup) comparisons over time. The models will also control for relevant covariates, including baseline outcome levels and number of standard drinks during the 60 days prior to participation. Various covariance structures (e.g., compound symmetry, autoregressive, etc.) will be tested, with final model selection based on fit statistics such as Akaike Information Criterion¹⁰⁹. Analyses will be conducted using SAS v9.4 (Cary, NC).

Hypothesis 1: Participants who receive oxytocin, as compared to placebo, will demonstrate significantly lower craving, aggression, physiological (HR, BP), and neuroendocrine (cortisol) reactivity to the TAP. To test this hypothesis, GLMMs with identity link functions (for continuous measures) and log link functions (for count data) will be used to model the between-group differences. Random couple effects will be used to account for within-couple correlation.

Hypothesis 2: Oxytocin response will be greater among women as compared to men. To test this hypothesis, GLMMs will be used to assess serially measured time points following medication administration (15, 30, and 60 minutes post task). The effects of gender, time, and their interaction will be assessed. Primary outcomes include alcohol craving, aggression, and cortisol.

Hypothesis 3: Oxytocin response will be lower among individuals with higher endogenous oxytocin levels and greater IPA severity. To test this hypothesis, alcohol craving, aggression, and cortisol levels will be examined as repeated measures variables using the strategies described above. Separate models will be conducted for endogenous oxytocin levels and IPA severity.

Randomization. Participants will be randomized to oxytocin or placebo. Because the extant literature suggests that the frequency and intensity of aggression in the TAP may be higher in men, on average, than women, a stratified randomization scheme will be used to ensure that groups are balanced by gender.

Sample Size Justification. Given the preliminary nature of this investigation, we aim to detect between-group differences in aggression measured by the TAP (oxytocin vs. placebo). Prior work¹¹⁰⁻¹¹² suggests that mean baseline aggression as measured within the TAP ranges from 2 to 4, with a standard deviation of 1.1 and with men having higher scores, on average, than women. With 50 couples (n=100) per group (and assuming alpha=0.05 and 2-sided hypothesis testing), we will have 80% power to detect moderate within-group changes (around 0.4 units [$\pm 10\%-20\%$] on the TAP shock intensity scale), consistent with our study hypotheses. We will have 80% power to detect moderate between-group differences (0.4 units) but with a larger alpha level (0.25), which is consistent with our pilot study framework.

Confidentiality and Data Security. All research personnel will attend a required in-service training conducted by [name] and [name] where the screening, informed consent, and assessment protocols will be described. The study protocol and safety plan will be printed and kept in a central location within the research space for easy access for all research staff. Standard operating procedures (SOPs) for the management of any participant or study-related emergency will be established and research staff will be trained on these protocols. All participant assessments will be scheduled during normal working hours beginning at 8am on the MUSC campus to ensure the presence of clinical staff and the safety of participants and

research staff. To protect participant confidentiality, all data will be stored in locked filing cabinets within a locked office and on MUSC's encrypted computers and data servers. All participants will be assigned a numerical study identifier to minimize the potential to link identifying information with study data. One master list of study participants will be kept separate from all other study data. Access to data will be restricted to research staff. Data will be maintained in a manner consistent with IRB-approved protocol. Only de-identified data will be used to present findings in presentations or publications. All research staff have or will complete the University of Miami CITI training course in the responsible conduct of research.

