of neurobiological risk and protective factors contributing to AUD and aggression, (b) more precisely elucidate associations between risk factors and IPA compared to existing daily diary and experience sampling methods^{5,39}, (c) examine aggression among both partners simultaneously, and (d) inform effective treatment development for AUD and IPA.

Oxytocin may help reduce craving and aggression. Accumulating evidence suggests that oxytocin may help reduce the effects of social stress on alcohol use behaviors^{49,56}. Few studies, however, have investigated the effects of oxytocin on human aggression. Oxytocin may help reduce IPA by reducing its known precipitating factors such as alcohol use, stress reactivity, and negative affect and by enhancing positive affect. No studies to date have examined the effects of oxytocin among individuals with AUD and co-occurring IPA. Further, accumulating evidence suggests that individual and contextual differences may influence concentrations of endogenous oxytocin and its effects on human behavior⁵⁷. The proposed study will address critical gaps in the literature by utilizing a well-controlled human laboratory paradigm (Taylor Aggression Paradigm) to examine the ability of oxytocin to reduce craving and aggression among couples with AUD and co-occurring IPA. We will compare subjective, physiological and neuroendocrine responses to the laboratory test within-subjects before and after they receive oxytocin or placebo, and between-subjects who receive either oxytocin or placebo. We will also examine individual, dyadic, and contextual factors that may influence oxytocin's effects on craving and aggression, which will help inform future translational research focused on the use of oxytocin among AUD and IPA populations.

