5.0 Inclusion and Exclusion Criteria/ Study Population

All participants will be at least 18 years of age or older. Women and members of minority groups will be eligible for participation.

Inclusion criteria indicate that participants must (a) aged 18-75, (b) fluent in English, (c) endorse at least one instance of mild or moderate physical IPA with their partner as defined by the Revised Conflict Tactics Scale (CTS-2)⁹⁷, (d) both partners must be willing to participate and (e) one or both partners must meet DSM-V diagnostic criteria for an alcohol use disorder (AUD). Concurrent substance use disorders (e.g., marijuana) is acceptable provided alcohol is the participant's primary substance of choice.

Exclusion criteria include (a) pregnancy or breastfeeding, (b) current or history of psychiatric or medical condition that could interfere with neuroendocrine function (e.g., hematological, endocrine, renal, or pulmonary disease; synthetic glucocorticoid or exogenous steroid therapy; psychotic, bipolar, eating disorders), (c) both partners with a BMI ≥ 39 , (d) current suicidal ideation and intent, (e) severe physical or sexual IPA in the past as defined by the CTS-2⁹⁷, (f) initiation of psychotropic medication in the past 4 weeks, (g) acute alcohol withdrawal as indicated by a score of 8 or greater on the CIWA-Ar⁹⁸, (h) a current or past diagnosis of epilepsy or history of seizures.

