Assessment Procedures. Following informed consent, eligible participants will complete a breathalyzer or saliva alcohol test, urine drug screen, blood draw, and pregnancy test (for women). Participants will have the option to participate in genomic research by providing an extra 7 milliliters of blood during the study blood draw. Participants will complete a psychosocial and medical history assessment (see Table 2). Note that for telehealth participants, biological specimens will not be collected, however, female participants will be required to take a pregnancy test (provided by study staff) and will be required to verbally confirm a negative result prior to continuing with any procedures. Provided that all inclusion and exclusion criteria are met, participants will be scheduled to complete the laboratory testing portion of the study.

Participants will be instructed to abstain from caffeine, nicotine, alcohol or other substances of abuse prior to the laboratory testing procedure. Smokers will be asked to abstain from smoking during study procedures and offered a nicotine patch prior to participation. Nicotine patch dosage will be determined by the number of cigarettes participants smoke daily (≥ 20 cigarettes/day=21mg; 10–19 cigarettes/day = 14 mg patch; 5–9 cigarettes/day = 7 mg patch).

Human Laboratory Procedure. Participants will complete an alcohol cue reactivity task and the TAP procedure approximately 45 minutes after receiving a 40 IU intranasal dose of oxytocin or placebo (i.e., saline). In a recent review of oxytocin studies, 40 IU is within the normal dosing range for humans and is one of the most common single dose concentrations utilized in human research⁷⁸. This literature indicates that a 40 IU dose is safe and effective in eliciting effects on HPA axis reactivity among participants with AUD^{78,79}.

Alcohol Cue Procedure. Consistent with the procedure developed by Monti and colleagues⁸¹, participants will spend 3 minutes holding and smelling a control beverage (water), and reactivity (e.g., craving, urge to use) will be assessed. Following a 3-minute rest period, participants' preferred alcoholic beverage will be presented and poured into an appropriate glass

and they will spend 3 minutes holding and smelling the beverage. Subjective and physiological reactivity will be measured again.

TABLE 2. ASSESSMENT MEASURES

Construct	Measure

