Eligibility	
 •Phone Screen Questionnaire •Demographics •Health History Interview & Concomitant Medications •Breathalyzer and Urine Drug Screen •Pregnancy (women only) •Mini International Neuropsychiatric Interview⁸² •Revised Conflict Tactics Scale; CTS-2⁸³ •Patient Health Questionnaire; PHQ-9⁹⁹
Dyadic Functioning	
 •Dyadic Adjustment Scale; DAS⁸⁷ •Emotional & Physical Infidelity⁸⁸
Substance Use	
 •Revised Clinical Institute Withdrawal Assessment; CIWA-Ar⁸⁹ •Time Line Follow back; TLFB^{90,91} •Alcohol Use Disorders Test;AUDIT⁹² •Drug Abuse Screening Test; DAST⁹³ •Fagerstrom Nicotine Dependence Test⁹⁴ •Marijuana Motives Questionnaire
Mental Health	
 •Traumatic Life Events Questionnaire; TLEQ⁹⁶ •PTSD Check List; PCL-5⁹⁷ •Childhood Trauma Questionnaire; CTQ⁹⁸ •Patient Health Questionnaire; PHQ-9⁹⁹ • Cognitive Emotion Regulation Questionnaire; CERQ-Short¹⁰¹ • Perceived Stress Scale -4; PSS-4¹⁰² • Interpersonal Sensitivity Measure;IPSM¹⁰³Impulsive Behavior Scale; UPPS
Neuroendocrine	
 •Endogenous Oxytocin (blood) Note: Collected unless staff learn of contraindications. •Cortisol (saliva) Note: Collected unless staff learn of contraindications.
Physiological	
 •Heart Rate (HR) •Blood Pressure (BP)
Subjective	•Visual Analogue Scale (VAS)

TAP Procedure. In the couple-specific TAP utilized in [name] (Consultant) is his ongoing NIAAA-sponsored trial, participants engage in a fictitious reaction time competition with their partner. Participants are led to believe that their partner chooses whether or not they receive a shock and its intensity. Participants have the option to administer a shock to their partner and its intensity in response to a "winning" trial. In reality, participants receive electric shocks in response to a "losing" trial at intervals randomly generated by the TAP software¹⁰⁴. IPA is operationalized as the number of shocks administered, intensity of the first "unprovoked" shock, proportion of maximum shocks selected, and average shock intensity. Each participant will receive the same number of shocks. Electric shocks are brief in duration (1 second), range in intensity from 25-250 mV, and are administered to two fingertips of the participant's non-dominant hand. The TAP task entails 30 trials for a total duration of 12-14 minutes.

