At the outset of the TAP procedure, the words "Get Ready" appear on the computer screen in front of the participant. Then the words "Press the Spacebar" appear on the screen. Participants press and hold the space bar until the words "Release the Spacebar" appear on the screen, at which time the participant will release the spacebar as quickly as possible. A "win" is indicated to the participant with the words "You Won. You May Give a Shock" appearing on the screen.

Following a winning trial, participants choose whether or not to shock their opponent and its intensity on a level ranging from 1 (very mild shock, definitely not painful) through 10 (intense shock, definitely painful). A “loss” is indicated with the words “You Lost. You Will Get a Shock” appearing on the screen. The shock intensity received by the participant is randomly selected by the computer software within the calibrated range specified for each participant.

Calibration: The finger stimulator apparatus (Colbourn Instruments, Whitehall, PA) is calibrated for each participant, controlling for individual differences in pain threshold that may influence shock selection. Two electrodes are attached to the participant’s middle and index finger on the non-dominant hand. Each participant is administered 1-second shocks that increase stepwise beginning with the lowest possible intensity. Participants are instructed to inform the researcher when the shocks are first detectable and then again when they experience a shock as painful. During the actual TAP procedure, shock levels range from 1 to 10 and correspond to the participant’s 55% through 100% pain threshold.

TABLE 3. LABORATORY TESTING

Duration	Procedure
Screening portion	
2-2.5 hours	Informed consent and assessment battery
30 minutes	Blood draw from nurse from Research Nexus
Laboratory portion	
Minute 0	Baseline measurement #1 (VAS, HR, BP, cortisol)
Minute 5	Baseline measurement #2 (VAS, HR, BP, cortisol)
Minute 10	Oxytocin or placebo administered
Minute 40	Post-medication assessment (VAS, HR, BP, cortisol)
Minute 45	Alcohol Cue
Minute 50	Post-Cue assessment (VAS, HR, BP, cortisol)
Minute 65	TAP
Minute 70	Immediate post-task assessment (VAS, HR, BP, cortisol)
Minute 85	15-minute post-task assessment (VAS, HR, BP, cortisol)
Minute 100	30-minute post-task assessment (VAS, HR, BP, cortisol)
Minute 130	60-minute post-task assessment (VAS, HR, BP, cortisol)
Minute 135	Participant debriefed, compensated and discharged

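### The plan tells the models to adjust for the baseline level of the outcome, but TAP aggression has no pre-dose value, so the rule cannot be applied to the outcome that sets the sample size

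*Combined protocol and SAP*

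**What the plan says.** The covariate rule in section 12.0 reads: "The models will also control for relevant covariates, including baseline outcome levels and number of standard drinks during the 60 days prior to participation". It comes before the hypotheses and carves out no outcome. Hypothesis 1 covers aggression alongside craving, heart rate, blood pressure and cortisol. Hypothesis 3 models aggression by the strategies already described.

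Section 10.0 defines the aggression outcome entirely from the TAP: "IPA is operationalized as the number of shocks administered, intensity of the first" unprovoked shock, the proportion of maximum shocks and the average intensity. The text places the alcohol cue task and the TAP "approximately 45 minutes after receiving a 40 IU intranasal dose of oxytocin or placebo". Table 3 puts dosing at minute 10 and the TAP at minute 65, and lists the TAP once.

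The pre-dose readings are at minutes 0 and 5. The first is "Baseline measurement #1 (VAS, HR, BP, cortisol"), and the second lists the same four items.

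The only mention of a baseline for aggression is in the sample size paragraph, where prior work is said to suggest that "mean baseline aggression as measured within the TAP ranges from 2 to 4, with a standard deviation of 1.1".

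Partner aggression is also recorded before the laboratory session, for eligibility (section 5.0), on the "Revised Conflict Tactics Scale (CTS-2").

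**The concern.** A covariate rule has to be executable for every outcome it governs. Here it works for craving, heart rate, blood pressure and cortisol, and fails for the outcome that sets the sample size. An analyst who reaches the aggression model must then decide, without guidance, whether to drop the term or find a substitute.

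Dropping it leaves a valid randomised comparison without baseline adjustment. A substitute taken from inside the TAP, such as the first shock, would be recorded after dosing. If oxytocin had already moved it, adjusting for it would remove part of the effect under test.

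The plan elsewhere reads as if a TAP baseline existed, which makes the second route easier to take. The sample size paragraph powers a within-group change on the TAP shock scale, and that needs a pre-dose TAP that Table 3 does not schedule.

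**Working it through.** **1. Which outcomes have a pre-dose value (Table 3)**

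| Outcome | Minutes 0 and 5 | Can the rule be applied? |
|---|---|---|
| Craving (VAS) | yes | yes |
| Heart rate, blood pressure | yes | yes |
| Cortisol | yes, where saliva is collected | yes |
| TAP aggression | no; TAP once at minute 65, dose at minute 10 | no |

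Section 2.0 agrees with the table: "We will compare subjective, physiological and neuroendocrine responses to the laboratory test within-subjects before and after they receive oxytocin or placebo". Aggression is not in that list.

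**2. The plan's own power figure**

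Inputs from section 12.0: difference 0.4, SD 1.1, 50 couples (100 people) per group, 80% power at alpha 0.25. The plan gives no within-couple correlation (ICC). With couples as the unit of randomisation, SE = 1.1 × √[(2/100)(1 + ICC)].

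- ICC 0: SE = 0.156 and 0.4/SE = 2.57. Power is 92.2% at two-sided alpha 0.25 and 72.9% at 0.05.
- ICC 0.3 (assumed): 86.5% and 61.6%.
- ICC 0.67 (solved for): SE = 0.201 and 0.4/SE = 1.99. Power is 80.0% and about 51%.

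So 80% is reproduced only with an unstated ICC of about 0.67. That is a separate matter and does not decide this point.

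**3. If a value from inside the TAP were used as the covariate**

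Assume the covariate has the same SD as the outcome and correlation r with it within arms, and that oxytocin shifts it by f × 0.4. The documents give neither r nor f.

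- Adjusted effect = 0.4 × (1 − r f), so the loss is 0.4 × r × f.
- Residual SD = 1.1 × √(1 − r²).

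| r | f = 0 | f = 0.5 | f = 1 |
|---|---|---|---|
| 0.3 | 0.40 (0% lost) | 0.34 (15%) | 0.28 (30%) |
| 0.5 | 0.40 (0%) | 0.30 (25%) | 0.20 (50%) |
| 0.7 | 0.40 (0%) | 0.26 (35%) | 0.12 (70%) |

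A simulation at r = 0.5 gave 0.402, 0.300 and 0.203 for f = 0, 0.5 and 1, matching the formula.

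Power at alpha 0.25 with ICC 0, against 92.2% unadjusted, is 86% to 88% at f = 0.5 and 47% to 77% at f = 1. At f = 0 it rises, because the covariate then only removes noise.

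**4. If a pre-dose covariate were used instead**

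Randomisation makes the arms equal in expectation on any pre-dose score, so the effect stays 0.40. With correlation rho between that score and the TAP outcome, the residual SD is 1.1 × √(1 − rho²). Gain in power, in percentage points:

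| ICC | Alpha | rho = 0.3 | rho = 0.5 |
|---|---|---|---|
| 0.67 | 0.25 | +2.6 | +7.5 |
| 0.67 | 0.05 | +3.8 | +12.0 |
| 0 | 0.25 | +1.7 | +4.3 |
| 0 | 0.05 | +3.9 | +11.4 |

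At rho = 0.3 the gain is about 2 to 4 points. At rho = 0.5 it is about 7 to 12 points at the ICC that reproduces the plan's 80%. It is smaller with ICC 0 and alpha 0.25, where power is already 92%. The plan gives no rho.

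**The case against.** The plan does not propose to adjust for anything recorded during the TAP. A reader might infer that it does from the phrase "mean baseline aggression as measured within the TAP ranges from 2 to 4", and conclude that the aggression analysis is biased toward zero. The documents do not support that. The sentence summarises earlier studies to obtain a mean and an SD, and defines no covariate for this trial. Section 10.0 lists the first unprovoked shock as an outcome index, not as a baseline. A halved effect needs three things at once: a covariate the plan never names, a full 0.4 shift in it, and an assumed correlation of 0.5. This part of the objection stands in full.

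The rule also speaks of relevant covariates, and it follows a sentence about comparisons over time. An analyst could fairly omit a term that does not exist, and the unadjusted comparison would not be biased by the omission. That stands as a likely outcome. It does not remove the gap, because the baseline level of the outcome is the first covariate named and Hypothesis 3 treats aggression as a repeated measure under the same strategies.

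The CTS-2 is an imperfect substitute. It is reported history, whereas the TAP is laboratory behaviour, and section 2.0 itself notes recall bias and disagreement between partners. Eligibility requires at least one mild or moderate physical act and excludes severe acts, which narrows the range and may weaken the correlation. Participants may decline any question (section 15.0), so some scores may be missing. The pre-dose VAS anger rating is another candidate. These points limit the expected gain. They do not make a pre-dose score invalid as a covariate.

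**Conclusion.** The point holds as a gap in specification. The baseline rule cannot be applied to TAP aggression, because no TAP value exists before dosing. That follows from Table 3 and the outcome definition and needs no assumption.

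The risk of bias is conditional. It arises only if a value from within the TAP is brought in to meet the rule, oxytocin has shifted that value, and it correlates with the outcome. The loss is then 0.4 × r × f, or 0% to 70% of the effect over r = 0.3 to 0.7 and f = 0 to 1. Both ranges are assumptions, as are equal SDs. No single figure in that range should be read as the expected loss.

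The correction is still worth making. It replaces a rule that cannot be executed for the sizing outcome, and it closes off a post-dose adjustment that the present wording leaves open.

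**What to change.** Replace the covariate sentence in section 12.0 with wording to this effect:

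> Models for craving, heart rate, blood pressure and cortisol adjust for the mean of the two pre-dose readings (minutes 0 and 5). Models for TAP aggression adjust for no value recorded during the TAP, since the TAP follows dosing; they adjust for the participant's CTS-2 physical-aggression perpetration score from the screening assessment. All models adjust for standard drinks in the previous 60 days.

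Add that where the same CTS-2 score serves as the Hypothesis 3 measure of IPA severity it enters the model once, and say how a missing score is handled. The sample size paragraph's within-group change on the TAP scale should be removed or reconciled with the single post-dose TAP.

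No new data are needed: the CTS-2 is already part of the eligibility assessment. The downside is one degree of freedom, and a gain in precision that may be small if the CTS-2 and the TAP are only weakly related.

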(8) For studies in which alcohol is administered, the DSM plan must indicate that NIAAA guidelines for the administration of alcohol will be followed. These guidelines can be found at the following web address: <http://www.niaaa.nih.gov/research/guidelines-and-resources/administering-alcohol-human-studies>.

The proposed study does not involve alcohol administration.

(9) If the study has a follow-up phase, there must be a specific plan for referral to treatment during follow-up of any patient requiring additional intervention due to significantly increased alcohol consumption or serious psychiatric/medical symptoms.

The proposed study takes place during one study visit and does not include a follow-up phase. All participants will be provided with a list of community resources upon study completion. Ineligible individuals presenting with serious mental or physical health symptoms including acute alcohol withdrawal will be referred clinically.

(10) The DSM plan must indicate that all adverse events and unanticipated problems during follow-up will be reported (SAEs within 48 hours) to the IRB and NIAAA.

Not applicable, as the proposed study does not include a follow-up phase.

(11) The DSM plan must briefly describe the procedures for data quality assurance and confidentiality.

A data analytic plan is outlined in the Data Analysis section. Because this study is a preliminary test of a new medication, we are interested in examining a broad range of outcome variables. The main outcome variables include alcohol craving, aggression, and subjective, physiological, and neuroendocrine reactivity to the laboratory procedure. Outcome data will be analyzed using chi-square, ANCOVA, and Poisson regression models. The alpha level for statistical significance will be set at .05.

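### The number of shocks cannot exceed the number of winning trials, but the only count model in the plan is log-link (Poisson where named), which can cost substantial power

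*Combined protocol and SAP*

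**What the plan says.** Section 10.0 (TAP Procedure) defines aggression by four indices and starts with a count: "IPA is operationalized as the number of shocks administered". The other three are two intensity measures and the proportion of maximum shocks. The length of the task is fixed ("The TAP task entails 30 trials"), and the chance to shock depends on winning: "Following a winning trial, participants choose whether or not to shock their opponent". The number of wins is not stated. Losing trials exist, so it is below 30. It appears to be the same for everyone, because "Each participant will receive the same number of shocks".

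For Hypothesis 1, Section 12.0 gives identity links to continuous measures and "log link functions (for count data" to the rest, and adds: "Random couple effects will be used to account for within-couple correlation". It names no count distribution. Section 13.0, item (11), does: "Outcome data will be analyzed using chi-square, ANCOVA, and Poisson regression models".

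The documents contain no binomial model, trial denominator, dispersion parameter or robust variance for this outcome.

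**The concern.** Section 12.0 does not say which outcome it means by count data. The other Hypothesis 1 outcomes are craving on a visual analogue scale, heart rate, blood pressure and cortisol, and the other three task indices are intensities and a proportion. The number of shocks is the only evident count, so it is the outcome that would receive the log link.

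That outcome is successes out of a limited number of opportunities. A Poisson model has no ceiling and sets the variance equal to the mean. The variance of a bounded count falls towards zero as people approach the ceiling, and rises again if people differ in how readily they shock. The Poisson standard error can therefore be too large or too small. The proportion of maximum shocks has the same bounded form and suits neither of the two listed links.

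What is at stake is the treatment test on one of the indices that define aggression. Section 12.0 lists aggression among the primary outcomes, and no index is named as the principal one.

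**Working it through.** **Inputs from the documents.** 30 trials; one decision to shock or not per win; 50 couples (100 people) per group; dyads as the randomised units; a random couple effect; two-sided alpha of 0.05.

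**Assumed, because not stated.** Wins m = 15 (range 10 to 29); probability p of shocking after a win, 0.1 to 0.9; correlation ρ among one person's decisions, 0 to 0.5.

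**The plan's own figure.** There is none for the number of shocks. The only between-group power figure (Section 12.0, Sample Size Justification) is 80% for 0.4 units of shock intensity, SD 1.1, alpha 0.25. By normal approximation, 0.4/(1.1√(2/100)) = 2.57 and 2.57 − 1.15 = 1.42, which gives 92.2% with independent people. With 50 couples per group as the unit it is 74.8%. The stated 80% needs an intraclass correlation of about 0.67, which is not given. That is a separate matter and does not bear on the count model.

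**Step 1: variance without a couple effect.** The true variance is m p(1−p)[1+(m−1)ρ]; the Poisson variance is m p. So

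Poisson SE / true SE = 1/√((1−p)[1+(m−1)ρ]).

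- With ρ = 0 the ratio is 1/√(1−p), whatever m is: 1.05 (p = 0.1), 1.20 (0.3), 1.41 (0.5), 1.83 (0.7), 3.16 (0.9).
- With m = 15 and p = 0.5 it is 1.08 at ρ = 0.05, 0.91 at 0.1, 0.73 at 0.2 and 0.62 at 0.3.
- The two SEs agree at ρ = p/((1−p)(m−1)). For p = 0.5 that is 0.111 (m = 10), 0.071 (m = 15) and 0.036 (m = 29). For p = 0.9 it is 1.0, 0.643 and 0.321.
- With m = 15, a Poisson distribution puts 0.5% (p = 0.5), 6.8% (0.7) and 28% (0.9) of its mass above the ceiling.

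**Step 2: what the couple effect changes.** Both partners share an arm, so the treatment comparison rests on couple totals. A random couple effect can add variance to those totals and so absorb most of the spread between people. It cannot take variance below the Poisson level. Ratios under 1 in Step 1 are therefore largely repaired; ratios over 1 are not.

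**Step 3: simulation of the planned model.** Poisson, log link, random couple intercept, m = 15, 50 couples per arm, no treatment effect, 250 replicates per setting. Couple and person effects are normal on the logit scale, with SDs shown as couple/person. Each cell is model SE divided by empirical SE, with type I error in brackets.

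| Mean shock rate | SD 0/0 | SD 0.5/0.5 | SD 1/1 | SD 0.5/1.5 |
|---|---|---|---|---|
| 0.27–0.33 | 1.08 (2.4%) | 1.02 (6.0%) | 0.86 (7.6%) | 0.91 (8.0%) |
| 0.45–0.50 | 1.46 (0.8%) | 1.08 (2.0%) | 0.94 (4.8%) | 1.00 (6.0%) |
| 0.63–0.74 | 1.93 (0.0%) | 1.12 (2.0%) | 1.05 (2.8%) | 0.98 (6.4%) |
| 0.84–0.89 | 2.64 (0.0%) | 1.78 (0.4%) | 1.06 (3.6%) | 1.02 (4.4%) |

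The Monte Carlo standard error at a true 5% is √(0.05×0.95/250) = 1.4 percentage points. A second simulation of the same model gave ratios of 1.3–3.2 with no heterogeneity and 1.1–2.1 with moderate heterogeneity (type I error 0–3.5%). Under large heterogeneity it gave 0.83–1.14 (type I error 1.5–9.5%).

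**Step 4: power.** This compares the planned Poisson mixed model with a binomial analysis using couple-level variance, at an effect that gives the latter about 80% (m = 15, 300 replicates per setting).

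| Shock rate, about | SD 0/0: Poisson v binomial | SD 0.5/0.5: Poisson v binomial |
|---|---|---|
| 0.5 | 53% v 78% | 81% v 81% |
| 0.75 | 21% v 81% | 74% v 78% |
| 0.9 | under 1% v 80% | 34% v 85% |

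With a person SD of 1.5 the two were about equal. Type I error of the binomial analysis was 3–7% throughout.

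**The case against.** **The plan does not commit this outcome to Poisson.** Section 12.0 names only a link, and Poisson appears in a general item of the monitoring plan. Section 12.0 also allows links to be adapted to the outcome type, and transformations or non-parametric methods. This stands in part: the plan is under-specified rather than firmly wrong. But the outcome types it lists are continuous, binary and count, which leaves this index a count, and the transformation clause is triggered by non-normality, not by a ceiling. A negative binomial model would not help near the ceiling either, since it too only adds variance to the Poisson.

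**People will differ.** Section 12.0 itself expects more frequent and more intense aggression in men. So the no-heterogeneity column is a limiting case, and wide spread removes most of the error. This stands.

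**The consequence is limited.** The number of shocks is one of four indices and the sample size rests on shock intensity. This also stands.

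**A stronger reading: false positives of 22–26%.** A reader might infer this from the Step 1 ratio of 0.62, since 1.96 × 0.62 = 1.22 gives a two-sided error of about 22%. A simulated Poisson fit without random effects reached 26%. The documents do not support it. Item (11) mentions no couple effect, but it refers to the data analysis section, and Section 12.0 requires one. With that effect, the same case (p = 0.5, ρ = 0.3) gave an SE ratio of 0.98 and type I error of 4.8–5.5%, fitted without individual-level covariates.

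**Another tempting inference: a biased group ratio.** If every participant has the same number of wins, as Section 10.0 suggests, leaving out the denominator does not bias the rate ratio. The problem is variance and range.

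**Conclusion.** The concern holds in a limited form. The plan gives a bounded count a log-link model, with Poisson the only distribution named, and makes no provision for the bound. It cannot be said that the standard errors are wrong, only that they may be. With the planned couple effect and 15 wins they are about right or mildly off when people differ widely, with type I error up to roughly 8–10%. They are about 1.3 to 3 times too large when most people shock on most wins and do not differ, and 1.1 to 2.1 times too large with moderate differences.

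The main risk is therefore a missed effect, not a false one. Its size rests on assumed values for wins, shock rate and spread, and on both partners receiving the same assignment. The shock-intensity power statement is unaffected. The change is worth making before analysis because it removes the dependence on these unknowns at almost no cost.

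**What to change.** In Section 12.0, Hypothesis 1, name the number of shocks and model it as events out of winning trials with a binomial GLMM (logit link). Include a random couple effect, and either a participant random effect or beta-binomial dispersion. State the number of winning trials.

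Treat the proportion of maximum shocks the same way. First state whether its denominator is wins or shocks given, because Section 10.0 does not say; use whichever defines the index.

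In Section 13.0, item (11), replace Poisson regression for these indices so that it agrees with Section 12.0.

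The cost is a different distribution in the GLIMMIX procedure that Section 12.0 already names, and effects reported as odds ratios rather than rate ratios. No data collection or sample size changes.
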